## **8.6 Statistical Analysis**

This section briefly describes the final study analyses. Detailed technical specifications of the statistical analyses will be described in a separate Statistical Analysis Plan.

### **8.6.1 Primary Analyses**

Study arms will be compared for baseline characteristics using descriptive statistics.

For each study visit, PrEP uptake will be defined as the proportion of TGW who initiate PrEP at any time up to and including that given visit among all TGW enrolled in the trial. PrEP uptake will be compared between study arms at the end of Week 26 for the primary objective. Confidence limits will be computed using the binomial distribution.

At each quarterly visit, the proportion of TGW adherent to PrEP is defined as the proportion of enrolled TGW who have confirmed protective levels of PrEP in their blood at that study visit. PrEP adherence (using either TDF or TAF-based regimens) will be **assessed objectively** using thresholds established by recently completed DOT studies. TGW who are missing drug level assessments, and who do not have drug dispensed at their most recent visit will be defined as non-adherent at that visit. The proportion of TGW determined to be adherent at Week 26 will be compared between the two study arms for the primary objective. Confidence limits will be computed using the binomial distribution.

PrEP persistence is defined as the average of each participant's mean number of visits adherent to daily PrEP. The mean number of visits adherent to daily PrEP will be (i) zero for TGW who never initiate PrEP during the study and (ii) the proportion of visits where the participant was confirmed to have protective levels of PrEP (using either TDF or TAF-based regimens) in blood according to objective thresholds established by recently completed DOT studies. PrEP persistence will be compared between study arms.

To assess acceptability in future use of the study intervention, the percentage (with 95% CI) of participants who report an interest in future use of co-located GAHT and peer-delivered health navigation model for HIV prevention in the future will be calculated among those enrolled in each study arm.

Descriptive summaries will be used to summarize and assess different aspects of feasibility such as recruitment, retention, and frequency and content of Peer Health Navigator contacts (text message, email, phone, in-person).

The proportion of individuals on each of the two PrEP agents (Truvada® vs Descovy®) will be reported at baseline, 13- and 26-week visits. If a significant imbalance is detected between arms at any of these visits, the primary analysis will be adjusted for PrEP agent using regression and/or causal inference methods. Similar strategies will also be employed if differential missingness is observed in each of the primary endpoints between the two arms.

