Participants who decline PrEP can remain in follow-up (see Section 6.4.1) and can begin PrEP at any time up to and including their Week 39 visit. Enrolling participants who decline PrEP at baseline allows for an assessment of the impact of the intervention on PrEP uptake over time. If a participant has not been provided PrEP on study by Week 39 and decides to initiate PrEP after the Week 39 study visit, PrEP will not be provided at the study site; rather the participant will be linked to local PrEP services (see Section 5.2 for details). Week 39 is the last visit before the end of the first year of the study which will provide information on PrEP uptake. The second year will provide information on PrEP persistence so PrEP cannot be initiated at the site but as noted, participants can be referred.

The multi-component interventional package including GAHT and PHN using SBCM is outlined in Table 3. During the first six months, the Deferred Intervention Arm includes standard HIV prevention interventions such as risk-reduction counseling (Project RESPECT; Prevention Cohort) and provision of PrEP. Participants in the Deferred Intervention Arm will be linked with institutions that have established a partner agreement with the site. A partner agreement at each site will include at a minimum an agreement to provide care to study participants in a timely manner.

Shown in Table 3 is each intervention component, a brief description, the theoretical foundation, and the staff member(s) responsible for component delivery.

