### **4.1 Inclusion Criteria**

TGW (assigned male at birth, trans-feminine spectrum – as defined in the SSP Manual – by self-report) who meet all of the following criteria are eligible for inclusion in this study.

1. Eighteen years or older at the time of screening.
2. Willing and able to provide informed consent for the study.
3. Interest in PrEP – as defined in the SSP Manual.

4. Non-reactive HIV test results at Screening and Enrollment.
5. Available to return for all study visits and within site catchment area, as defined per site's Standard Operating Procedures (SOP).
6. At risk for sexually acquiring HIV infection based on self-report of at least one of the following:
  - a) Any anal or vaginal sex with one or more serodiscordant or HIV-unknown serostatus sexual partners in the previous 3 months, regardless of condom use.
  - b) Anal or vaginal sex in exchange for money, food, shelter, or other goods or favors in the previous 3 months.
  - c) History of STI(s) in the past 6 months.
7. Willing to undergo all required study procedures.
8. General good health, as evidenced by the following laboratory values:
  - a) Calculated creatinine clearance  $\geq$  60 mL/minute using the Cockcroft-Gault equation.
  - b) Alanine aminotransferase (ALT) and aspartate aminotransferase (AST)  $<$  2.5 times the upper limit of normal (ULN.)
  - c) HBV surface antigen (HBsAg) negative.

*Note: Otherwise eligible participants with laboratory results outside the above-mentioned values, with the exception of those with reactive HIV test, can be re-tested during the screening window. Participants with reactive HIV tests will not be able to rescreen.*

*Note: Participants who practice receptive vaginal sex cannot be provided Descovy® as it is not approved for this indication.*

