### 8.3 Sample Size

There is limited data on PrEP uptake and adherence specific to the TGW population, with the published data being highly variable. Moreover, the TGW population is a hard to reach population requiring multiple sampling and recruitment strategies. Given the unique challenges described above, the sample size is determined on the basis of the statistical power to detect a hypothesized difference in proportions between the Immediate vs Deferred Intervention arms, taking logistical and operational constraints regarding recruitment of HIV-uninfected TGW into consideration.

Figure 5 shows the number of individuals needed per study arm to achieve 90%, 85%, and 80% statistical power to detect a pre-determined difference in proportions  $p_1 - p_0$  between the Immediate Intervention Arm vs the Deferred Intervention Arm, under 1:1 randomization, with  $p_1$  and  $p_0$  denoting the proportion of HIV-uninfected TGW satisfying the condition of interest in the Deferred and Immediate Intervention Arms respectively. The horizontal axis depicts a range of plausible values of  $p_1 - p_0$ .

**Figure 5.** Sample sizes needed to achieve power (80%, 85%, 90%) for a two-sided test in proportions for an individually randomized trial with 1:1 randomization based on different values of hypothesized differences in proportions. For PrEP adherence, the hypothesized value under the alternative is 0.2.

Current research on PrEP uptake is limited, although existing data show low rates of PrEP uptake among TGW. Among HIV-uninfected TGW randomized to the Immediate Intervention vs. Deferred Intervention Arms, the study is being powered to detect a 20 percentage-point difference in PrEP adherence and a 25 percentage-point difference in PrEP uptake between the Deferred Intervention Arm and Immediate Intervention Arm at Week 26. We assume that the uptake, adherence and retention rates will be the same for the two PrEP agents (FTC/TAF and FTC/TDF).

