We determine the conservative sample sizes needed to detect a difference of  $p_1 - p_2$  between proportion of HIV-uninfected TGW adhering to PrEP between the Deferred and Immediate Intervention Arms at week 26, targeting 90% power to detect statistically significant differences at the alpha 0.05-level based on a two-sided test in proportions. A total of 262 HIV-uninfected TGW will be needed to achieve 90% statistical power for detecting a difference in proportions of 20% adhering to PrEP between the Deferred vs Immediate Intervention Arms. This sample size also satisfies power requirements for PrEP uptake. Assuming an ~85% retention rate throughout the primary 6-month follow-up period, we will target enrolling total of approximately 310 HIV uninfected TGW individuals into study. Projected sample sizes are shown in Table 7. Equal 1:1 randomization is being used.

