#### 8.4 Accrual and Retention

Approximately 310 HIV-uninfected TGW will be enrolled and randomized to the Immediate and Deferred Intervention Arms across the five study sites. An average annual retention rate of at least 85 percent will be targeted. Differential enrollment targets will be considered for the sites, with higher enrollment targeted for the Brazil site and competitive enrollment among remaining U.S sites. We estimate 560 TGW will be screened for the study to achieve the enrollment target of approximately 310 TGW (80% of TGW screened).

a Considering that the variance, and therefore sample size is largest when  $p=0.5$ , we obtain conservative sample sizes by setting  $H_0: 0.5 - d/2$  and  $H_1: 0.5 + d/2$ , where  $d$  is the hypothesized difference in proportions between intervention and Deferred intervention arms.

b Note that since the hypothesized effect size for PrEP adherence is smaller than for PrEP uptake (20% vs 25%), the sample size needed to achieve 90% power based on PrEP adherence will also achieve greater power for PrEP uptake, hence powering the sample size for the prevention cohort study on PrEP adherence.

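### The Week 26 uptake comparison mixes PrEP starts at the Enrollment Visit with later starts and is not stratified by baseline willingness, so the arm difference may be compressed and power lost avoidably

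*Combined protocol and SAP*

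**What the plan says.** Section 8.6.1 defines the outcome cumulatively: "PrEP uptake will be defined as the proportion of TGW who initiate PrEP at any time up to and including that given visit", with all enrolled participants as the denominator. It then states that "PrEP uptake will be compared between study arms at the end of Week 26 for the primary objective". No covariate or stratum is named for this comparison. Section 8.6 leaves technical detail to a separate analysis plan.

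On who enters and what they are offered:
- Section 4.1, criterion 3, requires "Interest in PrEP", with the definition left to the SSP Manual. Section 5.2 does not require participants to accept PrEP.
- Section 3.1 and the Schema provide PrEP in both arms. Appendix Ia marks its provision at the Enrollment Visit. Table 3 lists PrEP education and provision as standard of care for everyone.
- Section 3.1 explains why decliners may enter: "Enrolling participants who decline PrEP at baseline allows for an assessment of the impact of the intervention on PrEP uptake over time".
- Section 6.3 equates enrollment with randomisation. Appendix Ia, footnote 5, starts peer navigation at the Enrollment Visit in the Immediate arm only. Hormones follow at an initiation visit up to 10 days after sampling.

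On size, Section 8.3 says "the study is being powered to detect a 20 percentage-point difference in PrEP adherence and a 25 percentage-point difference in PrEP uptake". Footnote a centres the assumed rates on 0.5, so uptake is taken as 37.5% versus 62.5%. Footnote b adds that "the sample size needed to achieve 90% power based on PrEP adherence will also achieve greater power for PrEP uptake".

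**The concern.** Someone who accepts PrEP at the Enrollment Visit is a Week 26 uptake responder from day 0. At that point no study hormones have been given, and in the Immediate arm navigation has only just begun. In a cohort selected for interest in PrEP, many may accept that day in either arm. Two things follow.

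First, the difference between arms is squeezed into whoever has not yet started. Centring the rates on 0.5 is conservative for variance, but it offers no protection against a ceiling. The low uptake that Section 1.1 cites (under 10%) is uptake in practice, in samples not described as selected for interest.

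Second, baseline willingness is likely to be the strongest predictor of the outcome. Leaving it out of the analysis lets a chance imbalance between arms pass straight into the estimate. A null uptake result would then be hard to read, in a study that Section 1.2 says will inform the size of a full efficacy trial.

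**Working it through.** **Plan's own figures.** Inputs from Section 8.3 and footnote a: two-sided alpha 0.05, power 90%, rates 0.5 ± d/2. Formula per arm: n = [1.960·√(2·p̄(1−p̄)) + 1.2816·√(p1(1−p1) + p0(1−p0))]² / d².
- Adherence, 0.40 vs 0.60: (1.3859 + 0.8879)² / 0.04 = 129.3, so 130 per arm and 260 in total (stated: 262). Power at 131 per arm is 90.4%.
- Attrition: 262 / 0.85 = 308.2, so 309 (stated: about 310).
- Uptake, 0.375 vs 0.625: (1.3859 + 0.8774)² / 0.0625 = 82.0, so 82 per arm. Power is 98.4% at 131 per arm and 99.4% at 155.

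The plan's numbers reproduce. Because uptake is counted among all enrolled, 155 per arm (310/2) is used below.

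**Ceiling.** The difference cannot exceed 1 − (Deferred-arm uptake). It falls below 25 points once Deferred-arm uptake passes 75%.

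**Compression.** The documents give no same-day start share, so s is assumed, and for this step it is taken as equal in both arms. With later start rates c1 (Immediate) and c0 (Deferred) among the rest, the difference is (1 − s)(c1 − c0).
- Gap c1 − c0 needed to reach 25 points, 0.25/(1 − s): 33 points at s = 25%, 50 at 50%, 62.5 at 60%, 83 at 70%, 100 at 75%.
- If the plan's 62.5% vs 37.5% applied only to those not starting that day: s = 25% gives 18.8 points and 93% power; s = 50% gives 12.5 points and 72%; s = 75% gives 6.3 points and 38%.

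**What remains detectable.** At 80% Deferred-arm uptake, the largest possible difference is 20 points, and about 12.6 points has 90% power with 155 per arm.

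**Gain from stratifying.** Let q be the share who say before randomisation that they intend to start that day. Assume that 95% of them start in both arms and that the others convert 50% vs 20% by Week 26.
- Unstratified variance term per arm: p(1 − p). Stratified: q·0.95·0.05 + (1 − q)·c(1 − c). SE = √(sum over arms / 155). Power ≈ Φ(difference/SE − 1.96).
- q = 60%: uptake 77% vs 65%, difference 12 points. Unstratified sum 0.1771 + 0.2275 = 0.4046, SE 0.0511, power 65%. Stratified sum 0.1285 + 0.0925 = 0.2210, SE 0.0378, power 89%.
- q = 70%: uptake 81.5% vs 72.5%, difference 9 points. Unstratified sum 0.3502, SE 0.0475, power 47%. Stratified sum 0.1895, SE 0.0350, power 73%.

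Simulation of the Mantel-Haenszel test under the same assumptions gives 65% rising to 87% and 47% rising to 70%, with type I error near 5%. The closed form is slightly optimistic, so the simulated values are the ones to use.

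**Weaker prediction.** If only 85% of intenders start (q = 60%), the sums are 0.2059 + 0.2419 = 0.4478 and 0.1765 + 0.1405 = 0.3170. The closed form then gives 61% rising to about 76%, a gain of 15 points where it was 24.

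**The case against.** The strongest reply is that the harm depends on a number that nobody has. No document states the same-day start rate, and the SSP Manual's definition of interest may be a weak filter. With 25% starting that day, 25 points remains attainable. This stands, and it limits the point to a risk.

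Same-day starts may also differ by arm. The study is open-label, randomisation comes first, and navigation begins that day in the Immediate arm only. As an illustration on assumed figures, same-day starts of 65% vs 50%, with the rest converting 50% vs 20%, give 0.65 + 0.35·0.50 = 82.5% vs 0.50 + 0.50·0.20 = 60%, a 22.5-point difference. This stands too. It is why same-day starters cannot be dropped, and why the ceiling is stated through Deferred-arm uptake.

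It can also be said that time to PrEP initiation is a primary endpoint in Section 8.2.1 and would separate early from late starts. That helps only in part, because Section 8.6.1 gives it no analysis. Drug-level confirmation is already covered by the separate adherence and persistence measures.

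A reader might infer more than the documents support:
- *That the sample size is wrong.* It is driven by adherence and reproduces, and footnote b is true for the 25-point effect it states.
- *That Section 3.1 places the uptake effect only in decliners.* It says that enrolling them allows uptake over time to be assessed. Comparing all randomised participants is consistent with that.
- *That the PrEP offer should come before randomisation.* Learning the arm may be part of how the strategy works, so moving the offer could remove some of the effect under study.

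**Conclusion.** The point holds as a risk to interpretation and as a cheap loss of precision. Two parts need no assumption: 25 points is arithmetically impossible above 75% Deferred-arm uptake, and the planned comparison ignores a likely strong baseline predictor. The size of the effect does depend on assumptions. With 60% to 70% intending to start, 95% of them starting in both arms and the others converting 50% vs 20%, stratifying adds about 22 to 23 points of power at 155 per arm. The gain is smaller if stated intention predicts starting less well.

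A reader might infer that the uptake comparison is bound to fail. The documents do not support that: the same-day rate is unknown, and differences well under 25 points can still be significant.

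**What to change.** Leave the PrEP offer and dispensing where they are, and keep the Week 26 uptake definition.

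1. Add one yes/no eCRF item, completed and saved immediately before the randomisation call: does the participant intend to start PrEP today?
2. In Section 8.6.1 and the analysis plan, compare Week 26 uptake in all randomised participants with a Mantel-Haenszel test and risk difference stratified by that item. Same-day starts stay in the outcome. The item is an analysis stratum only, so randomisation under Section 8.5 is unchanged.
3. Report uptake by arm within each stratum, including those who did not intend to start.

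Optionally, note in Section 8.3 that a 25-point uptake difference requires Deferred-arm uptake of at most 75%.

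The cost is one extra question before randomisation, a few lines of analysis text and a slightly more complex analysis. No additional visit, sample or participant is needed.

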### 3.1 Study Treatment Conditions

Eligible participants will be enrolled and will be randomized 1:1 to either the Immediate Intervention Arm or Deferred Intervention Arm (See Figure 1). Services for these arms will differ during the first 6 months of study participation.

Immediate Intervention Arm (0-6 months): Participants will be provided PrEP (Truvada® or Descovy®) and STI screening and treatment. The Immediate Intervention Arm will receive co-located services to begin after enrollment that include:

- Provision of GAHT and routine clinical monitoring
- PHN using SBCM

**Deferred Intervention Arm (0-6 months):** Participants will be provided PrEP (Truvada® or Descovy®) and STI screening and treatment. The Deferred Intervention Arm will receive linkage\* to services for the first 6 months.

- Linkage to GAHT and routine clinical monitoring
- Linkage to case management services

\* For this study, linkage is defined as the process of ensuring that study participants are connected with a local institution that provides GAHT services including treatment and monitoring. Wherever possible, linkages will be made with sites that can provide GAHT services at no cost to the participant. Each site will establish an agreement with one or more local institutions for this purpose and the agreement must be maintained throughout the study. Sites will develop an SOP describing the process for linkage of participants during the study or as needed once study concludes.

**Both Arms (6-18 months):** Participants will be provided PrEP (Truvada® or Descovy®) and STI screening and treatment. At the 6 month visit, all participants will be provided co-located care until they have reached 18 months of study participation at which time they will be linked to local services. This will include:

- Provision of GAHT and routine clinical monitoring
- PHN using SBCM

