#### **6.5 Visit Windows**

For each required study visit, there is an allowable visit window specifying on which study days (post-enrollment) the visit is "allowed" to be completed. The allowable visit windows are

contiguous from visit to visit, and do not overlap. Within each allowable visit window, there is a target visit window and study visits should ideally be conducted within this window. These windows are outlined in Table 6 below. If more than one visit is necessary to complete all visit procedures, these could be completed during multiple days within the allowable visit window.

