For participants randomized to Immediate Intervention Arm who accept GAHT starts at the Enrollment Visit. For participants randomized to the Deferred Intervention Arm who accept GAHT start up to 10 days following the Week 26 (Month 6) study visit.

These procedures apply to GAHT Initiation Visit for both study arms. To be scheduled up to 10 days after collection of samples for estradiol and total testosterone samples for provision of GAHT as described in the protocol.

PHN starts at the Enrollment Visit for participants randomized to the Immediate Intervention Arm, and at Week 26 (Month 6) for participants randomized to the Deferred Intervention Arm.

Total cholesterol, HDL, triglycerides, and LDL (either calculated or measured). Participants should have fasted for at least 8 hours, preferably 12 hours, prior to sample collection. If participants are not fasting, do not order the lipid testing and reschedule the participant to return to the same for lipid sample collection: if not collected at the Screening Visit, sample should be collected prior to the Enrollment Visit; if not collected at Weeks 26 or 78, sample should be collected ideally within 72 hours of the visit.

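### The primary Week 26 uptake count includes PrEP starts at the visit where the Deferred arm crosses over, which can shrink the difference between arms

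*Combined protocol and SAP*

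**What the plan says.** Section 8.6.1 counts as uptake every participant who has managed to "initiate PrEP at any time up to and including that given visit among all TGW enrolled in the trial". It then states that "PrEP uptake will be compared between study arms at the end of Week 26 for the primary objective".

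The control condition ends at the same visit. Section 3.1 says: "At the 6 month visit, all participants will be provided co-located care". Appendix Ia, footnote 5, starts peer navigation "at Week 26 (Month 6) for participants randomized to the Deferred Intervention Arm". Hormone provision for that arm comes slightly later: footnote 3 allows up to 10 days "following the Week 26 (Month 6) study visit".

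PrEP can be started at Week 26. Appendix Ia schedules its provision there, and Sections 3.1 and 5.2 allow a first start through Week 39. Section 6.5 says that when one day is not enough for all procedures, "these could be completed during multiple days within the allowable visit window". Table 6 sets that window for Week 26 at Day 154 to 244. No text orders the procedures within the visit or fixes PrEP status before navigation begins.

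**The concern.** Section 1.2 explains the deferred design as a comparison of people who receive the intervention with people who have not yet received it. The uptake count closes after that contrast has ended. A Deferred participant without PrEP may meet her navigator at Week 26, hear that hormones are now available on site, and start PrEP at that visit. She is then a success for the control arm.

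Only the Deferred arm receives something new at Week 26, so the extra starts fall on one side. Uptake is a named primary comparison with its own 25-point target (Section 8.3). Section 1.2 also says the trial is to inform the sample size of a full efficacy trial, so an understated uptake difference would carry forward into that plan.

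**Working it through.** **Inputs.** From Sections 8.3 and 8.4 with the sample-size footnotes: two-sided alpha 0.05; power 90%; differences of 0.20 (adherence) and 0.25 (uptake) at Week 26; proportions centred on 0.5; 131 evaluable per arm; about 310 enrolled, so 310 / 2 = 155 per arm. Section 8.6.1 takes all enrolled as the uptake denominator, so 155 is the closer figure for uptake. Results are given for both.

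**Reproducing the plan's figure.** For adherence, 0.40 vs 0.60, without continuity correction:

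n = [1.960·√(2·0.5·0.5) + 1.282·√(0.4·0.6 + 0.6·0.4)]² / 0.20² = 129.3, so 130 per arm or 260 in total.

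Using variance 0.25 in both terms gives 131.3 per arm. The stated 262 is reproduced within rounding and choice of formula. 262 / 0.85 = 308.2, so 309 against the stated 310. The sample size is not in error.

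**Effect of the counting rule.** Let g be the excess in Deferred uptake, as a share of the whole arm, caused by crossover at the Week 26 visit. The documents give no value for g; those below are assumptions. Take planned uptake as 0.375 (Deferred) and 0.625 (Immediate). The observed Deferred proportion is then 0.375 + g and the expected difference is 0.25 − g. With p1 = 0.375 + g, p2 = 0.625, d = p2 − p1 and p̄ their mean:

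power = Φ{ [d·√n − 1.960·√(2·p̄·(1 − p̄))] / √(p1(1 − p1) + p2(1 − p2)) }

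Example, g = 0.10, n = 131: d·√n = 1.717; the null term is 1.960 × 0.7036 = 1.379; the denominator is 0.6955; (1.717 − 1.379) / 0.6955 = 0.486; power = 68.6%.

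| g | g / 0.625 (share of Deferred participants not yet on PrEP) | Difference | Power, 131 per arm | Power, 155 per arm |
|---|---|---|---|---|
| 0 | 0% | 0.25 | 98.4% | 99.4% |
| 0.02 | 3.2% | 0.23 | 96.5% | 98.4% |
| 0.05 | 8% | 0.20 | 90.5% | 94.5% |
| 0.10 | 16% | 0.15 | 68.6% | 75.9% |
| 0.15 | 24% | 0.10 | 37.3% | 42.9% |

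Power falls below 90% once g exceeds about 5.2 points at 131 per arm, or 6.8 at 155. It falls below 80% at about 7.8 or 9.2 points.

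**Adherence.** Week 26 adherence is judged by drug level. Section 6.7 explains that tenofovir diphosphate in dried blood spots (DBS) reflects average exposure over preceding months. A start on the visit day can hardly move it.

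**The case against.** Several points on the other side stand.

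- **The new stimulus on the day is limited.** Table 3 lists PrEP education for all participants throughout the study, with peer navigators among those delivering it. Hormones follow up to 10 days later. What is new at Week 26 is strengths-based navigation and the offer of co-located care.
- **Only the excess is bias.** Some Deferred participants would have started at Week 26 anyway, and the Immediate arm has Week 26 starts too. A reader might assume that 30 to 50% of the Deferred arm is unstarted and that 20 to 40% of these start at the visit, giving 0.30 × 0.20 = 6 to 0.50 × 0.40 = 20 points of contamination. The documents support none of those rates, and the product is a gross count of starts. Interest in PrEP is an entry criterion (Section 4.1), and these participants would have gone without PrEP since enrollment.
- **Weeks of contamination are not established.** One might infer that prompted starts up to Day 244 all count as Week 26. Section 6.4.2 requires laboratory results before dispensing, so some starts will come after the visit day, but no text assigns a later dispensing date to the Week 26 visit. The primary comparison time can also be read as a calendar cut-off. This is an ambiguity to settle.
- **Other pre-crossover information exists.** It is tempting to say that the only randomized contrast is compromised. Uptake is defined at every visit, so Week 13 is also randomized and lies wholly before crossover.
- **The bias is conservative.** It cannot produce a false positive: if the services have no effect, they prompt no extra starts.

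Section 8.6 leaves technical detail to a separate analysis plan. But 8.6.1 already states this definition, and nothing in the supplied text corrects it. These points limit the size of the problem; they do not remove it.

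**Conclusion.** The concern holds as a matter of definition and timing. As written, the primary Week 26 uptake count can credit starts prompted by crossover to the control arm, which shrinks the difference if the intervention works. The size cannot be derived from the documents. On the 0.375 vs 0.625 assumption, an excess of up to about 5 points still leaves power near or above 90%, while 10 points cuts it to roughly 69 to 76%. The estimate is biased at any excess above zero, whatever the power. The sample size calculation stands, and the adherence comparison behind it is largely untouched. The change should be made because it is cheap and the time point is primary.

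**What to change.** In Section 8.6.1, for the primary between-arm uptake comparison, count in both arms only PrEP starts dated before the first day of the participant's Week 26 visit and no later than one common study day. Day 182, the target day in Table 6, would serve, and would also apply to those who miss the visit. Use the same cut-off when arms are compared on time to PrEP initiation (Section 8.2.1). Report the present definition, with Week 26 visit starts included, as a sensitivity analysis.

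As a secondary safeguard, state in Appendix Ia that Week 26 DBS, the ACASI questionnaire and PrEP status are recorded before the first PHN or co-located hormone contact in the Deferred arm.

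Cost: a sentence or two in 8.6.1 and a footnote in Appendix Ia. N need not change: if the planned 0.375 vs 0.625 holds at the earlier cut-off, power is 98.4% at 131 per arm and 99.4% at 155. The real price is that starts made at the Week 26 visit leave the primary figure in both arms. That visit is one of three scheduled PrEP provision visits by then (Enrollment, Week 13, Week 26), so genuine Immediate-arm starts will be lost. Some unevenness also remains: a visit held between Day 154 and Day 181 closes the count earlier than Day 182, so the timing of Week 26 visits should be reported by arm.
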